HCQ has been shown to cause severe hypoglycemia including loss of consciousness that could be life threatening in patients treated with or without antidiabetic medications. Patients treated with HCQ should be warned about the risk of hypoglycemia and the associated clinical signs and symptoms. Patients presenting with clinical symptoms suggestive of hypoglycemia during treatment with HCQ should have their blood glucose checked and treatment reviewed as necessary.

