3.1.1 Dose Limiting Toxicity (DLT) (Safety Run-In only)

The DLT period is one cycle, 28 days, starting on Day 1 of cycle 1 after study drugs administration.

The following events will be considered DLTs (CTCAE v5.0) if attributable (definite, probable, possible) to the combination of study drugs:

Toxicity Category	DLT Criteria (grade per CTCAE 5.0)
Hematology	Grade ≥ 4 neutropenia lasting ≥ 7 consecutive days and/or not resolving within 48 hours to a grade 2 or less toxicity after correctible treatment
	Grade ≥ 4 thrombocytopenia lasting ≥ 7 consecutive days and/or not resolving within 48 hours to a grade 2 or less toxicity after correctible treatment
	Grade ≥ 3 neutropenia with fever (temperature ≥ 38.5 °C), not correctible within 48 hours to a grade 2 or less toxicity
Skin and subcutaneous tissue disorders	Grade ≥ 3 rash, hand-foot skin reaction or photosensitivity lasting > 7 consecutive days and/or not resolving within 48 hours to a grade 2 or less toxicity after correctible treatment
Eye disorders	Grade ≥ 2 retinal events lasting > 14 consecutive days confirmed by ophthalmologic examination
	Grade ≥ 3 retinal events confirmed by ophthalmologic examination, not correctible within 48 hours to a grade 2 or less toxicity
Gastrointestinal	Grade ≥ 3 nausea or vomiting lasting ≥ 7 days and/or not resolving within 48 hours to a grade 2 or less toxicity after correctible treatment
	Grade ≥ 3 diarrhea lasting ≥ 7 days and/or not resolving within 48 hours to a grade 2 or less toxicity after correctible treatment

	Grade \geq 3 total bilirubin not related to progression of disease, not correctible within 48 hours to a grade 2 or less toxicity
	Grade \geq 3 AST or ALT (isolated increases in AST without concomitant increases in ALT will not be considered DLT because of the non-specific nature of AST), not correctible within 48 hours to a grade 2 or less toxicity.
Hepatic	Patients with liver metastases will require AST or ALT levels 10 x ULN (isolated increases in AST without concomitant increases in ALT will not be considered DLT because of the nonspecific nature of AST).
	Grade \geq 4 alkaline phosphatase lasting \geq 7 consecutive days and/or not resolving within 48 hours to a grade 2 or less toxicity after correctible treatment
ECG QT Interval	QTcF interval \geq 501 ms on at least two separate ECGs, not correctible within 48 hours to a grade 2 or less toxicity

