Renal	Serum creatinine $> 2 \times$ ULN, not correctible within 48 hours to a grade 2 or less toxicity
Exceptions to DLT criteria	Grade 3 alopecia
	< 5 days of Grade 3 fatigue
	< 5 days of Grade 3 edema
	Grade \leq 4 lymphopenia
	Grade \leq 4 laboratory abnormalities that are responsive to oral supplementation or deemed by the investigator to be clinically insignificant.

3.1.2 Safety Run-In:

Six patients will be enrolled in a staggered fashion with at least 7 days minimum between each patient enrolled. If < 2 patients experience DLTs, as defined in section [3.1.1](#), we will proceed to the following portion of the trial. If ≥ 2 patients experience DLT, we will stop enrollment and will submit next amendment with new study design.

Subjects who do not start or do not complete the DLT observation period for reasons other than a DLT will be replaced and not included in the evaluation.

In case of DLT, DLT will be documented and patient, per PI discretion, may continue study treatment if toxicity could be managed by interruption of study treatment or dose reductions (See Section [3.3](#)).

Patient will be eligible for the DLT evaluation if at least ≥ 80 percent of trametinib and HCQ scheduled doses were taken within the DLT period.

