Renal Serum creatinine \geq Grade 2	Check cystatin-C levels. If GFR calculated by cystatin C is \geq 30 mL/min/1.73 m ² , continue HCQ and trametinib. If GFR calculated by cystatin C is \leq 30 mL/min/1.73 m ² , hold HCQ and trametinib. Monitor with weekly CMP and cystatin C until AE resolves to \leq Grade 1. Restart study drugs, with HCQ at next lower dose level.	Check cystatin-C levels. If GFR calculated by cystatin C is \geq 30 mL/min/1.73 m ² , continue HCQ and trametinib. If GFR calculated by cystatin C is \leq 30 mL/min/1.73 m ² , discontinue HCQ and trametinib.* *2nd occurrence of elevated serum creatinine will only be determined if 1st occurrence included elevated cystatin C and dose reduction.
Hypoglycemia	Hold HCQ if Grade 2. Monitor AE until resolution to Grade \leq 1. Restart study drugs, with HCQ at next lower dose level. Hold HCQ if Grade 3. Monitor AE until resolution to Grade \leq 1. Restart study drugs HCQ at next lower dose level. Discontinue HCQ permanently if Grade 4	Discontinue HCQ and trametinib
Non-hematologic events Grade \geq 3, except for the exclusions noted below: • Grade 3 alopecia • < 5 days of Grade 3 fatigue • < 5 days of Grade 3 edema • Grade 3 laboratory abnormalities that are responsive to oral supplementation	Hold HCQ and trametinib. Monitor AE until resolution to Grade \leq 1. Restart study drugs, with HCQ at next lower dose level.	Discontinue HCQ and trametinib

Adverse Event	1 st Occurrence	2 nd Occurrence
or deemed by the investigator to be clinically insignificant		

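### The closed DLT list in 3.1.1 lacks the general Grade ≥3 non-hematologic row that its own exceptions presuppose, so some events that permanently stop a drug do not count toward the 2-of-6 run-in rule

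*Combined protocol and SAP*

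**What the plan says.** Section 3.1.1 introduces its table with "The following events will be considered DLTs (CTCAE v5.0) if attributable (definite, probable, possible) to the combination of study drugs". The rows cover hematology, skin, retinal events, nausea/vomiting and diarrhea, bilirubin, transaminases and alkaline phosphatase, QTcF, and creatinine. There is no wording such as 'including' or 'other'. The exceptions that follow include Grade 3 alopecia, "< 5 days of Grade 3 fatigue" and the same for edema. On timing: "The DLT period is one cycle, 28 days, starting on Day 1 of cycle 1".

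Section 3.1.2 enrolls six patients. It proceeds if fewer than two have a DLT as 3.1.1 defines it, and otherwise stops for redesign. Patients who do not start or complete the observation period "for reasons other than a DLT will be replaced and not included in the evaluation". A patient is eligible for the evaluation only if at least 80 "percent of trametinib and HCQ scheduled doses were taken within the DLT period".

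Table 4 (3.3.2) has a row for non-hematologic events of Grade ≥3, "except for the exclusions noted below", and those exclusions contain the same alopecia, fatigue and edema items. Its hypoglycemia row says "Discontinue HCQ permanently if Grade 4". Table 6 (3.3.3) permanently stops trametinib for symptomatic cardiomyopathy, an LVEF fall >20% that is below LLN, life-threatening PE, and ILD/pneumonitis.

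**The concern.** The run-in is the trial's only numeric safety gate, and 1.2.6.3 says that no toxicity data exist for this doublet. The gate should count the events that the protocol itself treats as intolerable, and for several it does not. Cardiomyopathy is a stated risk of both drugs (1.2.5.2, 1.2.6.2), yet the only cardiac row is QTcF. Section 1.2.6.2 also warns that "HCQ has been shown to cause severe hypoglycemia including loss of consciousness that could be life threatening", yet hypoglycemia has no row.

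At stake is the count. A run-in with one listed DLT and one related life-threatening PE scores 1 of 6, and enrollment proceeds.

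**Working it through.** The documents state no operating characteristic for the run-in, so there is no figure to reproduce. The check sets the sections side by side and then sizes the effect.

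**1. Events that permanently stop a drug at first occurrence, against the 3.1.1 rows**

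| Event | Source of the stop | Row in 3.1.1 |
|---|---|---|
| Symptomatic cardiomyopathy | Table 6 | none |
| LVEF fall >20% that is below LLN | Table 6 | none |
| Life-threatening PE | Table 6 | none |
| ILD/pneumonitis | Table 6 | none |
| Grade 4 hypoglycemia | Table 4 | none |
| Retinal vein occlusion | Table 6 | can meet the retinal rows |
| Severe cutaneous reactions | Table 6 | at most partly, by the rash row |

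The alopecia, fatigue and edema exceptions modify no row in 3.1.1 but fit the general row in Table 4. The likeliest explanation is that this row was left out of 3.1.1.

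**2. How such a patient is scored**

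The echocardiogram is due at C2D1. The calendar in 3.4 (footnotes 1 and 6) allows a cycle of 28 ± 3 days and places evaluations within 3 days before Day 1. C2D1 is therefore Day 26 to 32, and the echo falls on Days 23-25 (25-day cycle), 26-28 (28-day) or 29-31 (31-day).

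- A hold starting at an echo on Day 24 or later leaves at least 23/28 = 82.1% of trametinib doses. The patient is evaluable and scored as having no DLT.
- An echo on Days 29-31 falls outside the fixed 28-day window.
- A hold of 6 days leaves 22/28 = 78.6% of trametinib and 44/56 = 78.6% of HCQ doses. The patient is then non-evaluable, and is replaced if the observation period is not completed.

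**3. Size for LVEF**

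Input: 5 of METRIC's 14 cardiomyopathy cases among 211 patients were found in month 1 (1.2.5.2). p = 5/211 = 0.0237, Clopper-Pearson 95% CI 0.0077 to 0.0544.

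- P(≥1 of 6) = 1 − (1 − p)^6 = 13.4%, about 5% to 29% over the CI.
- P(≥2 of 6) = 1 − (1 − p)^6 − 6p(1 − p)^5 = 0.8%.
- Given one listed DLT, P(at least one of the other five) = 1 − (1 − p)^5 = 11.3%, or about 24% at the upper limit.

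METRIC cases leading to discontinuation were 4/211 = 1.9%, over all treatment.

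**4. Other events**

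No first-cycle rate is given for PE, hypoglycemia or related death. For ILD/pneumonitis the reported onset range with trametinib is 60 to 172 days (1.2.5.2), so a first-cycle case would be unusual on that evidence. In Table 3, 5 of 12 Grade 3 counts have no 3.1.1 row (chills 1, fever 1, dehydration 2, ejection fraction 1). That is a triplet with dabrafenib, with timing not stated.

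**5. Effect of counting the events on P(stop)**

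Let L be the listed-DLT rate and u the added rate, both assumed and taken as independent. P(stop) = P(≥2 of 6) at rate 1 − (1 − L)(1 − u).

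| L | now | u = 1.9% | u = 2.4% | u = 5% |
|---|---|---|---|---|
| 5% | 3.3% | 5.8% | 6.5% | 10.9% |
| 10% | 11.4% | 14.9% | 15.8% | 21.2% |
| 20% | 34.5% | 38.2% | 39.1% | 44.2% |

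**The case against.** **Implied catch-all.** The exceptions make sense only if other Grade ≥3 events were meant to count, so a sensible investigator might count them. That supports an omission as the cause, but no positive criterion says that they count, and 3.1.2 ties the rule to 3.1.1.

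**Other safeguards.** Dose rules still apply to each patient. Run-in patients are staggered by at least 7 days (3.1.2), the team discusses each patient weekly (7.3), deaths within 30 days not due to progression are reported within one business day (7.2.3), and the study may be suspended for unacceptable risk (13.1). This stands: individual patients are protected. None of these measures sets a threshold or feeds the 2-of-6 count.

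**Small effect.** Nine of METRIC's 14 cardiomyopathy cases came after month 1, with median onset at 63 days, so no 28-day list would catch them. The 5/211 carries no grade and may include cases below any stop threshold. Both points stand and limit the size.

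**Replacement.** A reader might infer that every patient with an unlisted event is replaced. Section 3.1.2 replaces only those who do not start or complete the observation period; a patient on hold can still complete it.

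**A wider reading of the tables.** A reader might infer that Tables 4 and 6 permanently stop a drug for any LVEF loss, any thromboembolism or any severe non-hematologic event. They do not. Uncomplicated DVT/PE is withheld for up to 3 weeks and asymptomatic LVEF decline for up to 4. Table 4's general row is hold and restart, with discontinuation at the second occurrence. Death is a row in neither table.

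**Conclusion.** The point holds for the five named first-occurrence stops and for a related death from an unlisted cause. Following 3.1.1 and 3.1.2 as written, none of these counts toward the stop rule, so the gate can pass with a count that is too low. The gap concerns the gate, not the care of individual patients.

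The size that can be shown is modest: for LVEF alone, about a 13% chance of at least one case in six (5-29%) and 0.8% for two or more. These figures assume that METRIC's single-agent month-1 rate applies. It would be tempting to read 13%, or the 11% conditional on one listed DLT, as ceilings. They are point estimates for trametinib alone in melanoma, and the documents give no bound for trametinib with HCQ in this population. The effect of the whole unlisted class cannot be computed without assumed rates. The change is worth making because it is cheap and the gate has only six patients.

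**What to change.** In 3.1.1 add three rows:

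- (a) any treatment-related death;
- (b) related symptomatic cardiomyopathy, LVEF fall >20% that is below LLN, life-threatening PE, ILD/pneumonitis or Grade 4 hypoglycemia;
- (c) any other related Grade ≥3 non-hematologic event not covered by an existing row and not correctible within 48 hours to Grade 2 or less, subject to the listed exceptions.

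Name the events in (b) rather than pointing to every discontinuation outcome in Tables 4 and 6. Several of those depend on non-improvement after 3 to 4 weeks of withholding and often cannot be settled in 28 days. A blanket reference would also override the grade and duration limits in the eye rows for retinal vein occlusion. Leave the eye and skin rows unchanged.

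In 3.1.2 state that a patient with a DLT counts whatever percentage of doses was taken and is not replaced, and that the run-in C2D1 echocardiogram result counts toward the DLT evaluation.

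The cost is three rows and two sentences, with no new procedure. An echo as late as Day 31 delays that patient's evaluation by up to 3 days. The run-in also becomes somewhat more likely to stop: from 11.4% to about 15-16% at an assumed 10% listed-DLT rate and a 1.9-2.4% added rate, and more if unlisted events are commoner. The 48-hour condition in (c) keeps brief, correctible events out and limits that increase.

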3.3 Dose Modifications/Delay

In case of unbearable toxicity definitely attributed to one of the study drugs, patient will be taken off this drug and per PI discretion may continue treatment with the other drug only.

When, at the beginning of a treatment cycle, treatment delay related to one of the drugs is indicated, both study drugs should be held and resumed concurrently.

If, in the opinion of the investigator, a toxicity is considered to be due solely to one drug, the dose of the other drug may not require modification per PI discretion.

Dose interruptions for study treatment-related AEs are allowed as per the dose modification recommendations. Doses of any investigational product that were not administered due to toxicity will not be replaced within the same cycle. In addition to dose interruption, the need for a dose reduction at the time of treatment resumption should also be considered based on the dose modifications recommendations. If a toxicity-related dose delay of HCQ and trametinib for >28 days is required, treatment will be discontinued permanently, and the patient should be removed from study treatment.

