3.3.2 Hydroxychloroquine

Table 4 Guidelines for hydroxychloroquine-related toxicities

Adverse Event	1 st Occurrence	2 nd Occurrence
Hematology Grade 4 neutropenia lasting \geq 7 consecutive days Grade 4 thrombocytopenia \geq 7 consecutive days Grade \geq 3 neutropenia with fever (temperature \geq 38.5 °C)	Hold HCQ and trametinib. Continue weekly hematologic monitoring. Once AE resolves to \leq Grade 1, restart study drugs, with HCQ at next lower dose level.	Discontinue HCQ and trametinib
Skin and subcutaneous tissue disorders Grade \geq 3 rash, hand-foot skin reaction or photosensitivity lasting $>$ 7 consecutive days despite skin toxicity treatment	See Table 5	Discontinue HCQ and trametinib
Eye disorders Grade 2 retinal events lasting $>$ 14 consecutive days confirmed by ophthalmologic examination Grade \geq 3 retinal events confirmed by ophthalmologic examination	Hold HCQ and trametinib. Monitor until AE resolves to Grade \leq 1. Patients should be referred for ophthalmologic exam. Restart study drugs, with HCQ at next lower dose level.	Discontinue HCQ and trametinib
Gastrointestinal Grade \geq 3 nausea or vomiting lasting \geq 7 days despite optimal anti-emetic therapy	Hold HCQ and trametinib. Monitor until AE resolves to Grade \leq 1. Restart study drugs, with HCQ at next lower dose level.	Discontinue HCQ and trametinib
Grade \geq 3 diarrhea lasting \geq 7 days despite optimal anti-diarrhea treatment	See Table 6	Discontinue HCQ and trametinib
Hepato-biliary Grade \geq 3 total bilirubin felt to be not related to progression of disease Grade \geq 3 ALT (isolated increases in AST without concomitant increases in ALT will not be considered dose-limiting because of the non-specific nature of AST) Grade 4 alkaline phosphatase lasting \geq 7 consecutive days felt to be not related to progression of disease	Hold HCQ and trametinib. Monitor with weekly CMP until AE resolves to Grade \leq 1. Restart study drugs, with HCQ at next lower dose level.	Discontinue HCQ and trametinib
ECG QT Interval	Hold HCQ and trametinib. Monitor	Discontinue HCQ

Abbreviated Title: Trametinib and HCQ in BTC**Version Date: 04/06/2022**

Adverse Event	1 st Occurrence	2 nd Occurrence
QTcF interval \geq 501 ms on at least two separate ECGs	with ECG until AE resolves to Grade \leq 1. Restart study drugs, with HCQ at next lower dose level.	and trametinib

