3.3.3 Trametinib

Dose reductions for adverse reactions associated with trametinib are presented in **Table 5**

Table 5: Recommended Dose Reductions for Trametinib for Adverse Reactions

Action	Recommended Dose
First Dose Reduction	1.5 mg orally once daily
Second Dose Reduction	1 mg orally once daily
Subsequent Modification	Permanently discontinue if unable to tolerate trametinib 1 mg orally once daily

Dosage modifications for adverse reactions associated with trametinib are presented in **Table 6**.

Table 6 Recommended Dosage Modifications for Trametinib for Adverse Reactions

Severity of Adverse Reaction ^a	Dosage Modification for Trametinib ^b
Venous Thromboembolism	
Uncomplicated deep venous thrombosis (DVT) or pulmonary embolism (PE)	Withhold trametinib for up to 3 weeks. 
• If improved to Grade 0-1, resume trametinib at lower dose.• If not improved, permanently discontinue trametinib.
Life threatening PE	
Cardiomyopathy	Permanently discontinue trametinib.
Asymptomatic, absolute decrease in left ventricular ejection fraction (LVEF) of 10% or greater from baseline and is below institutional lower limit of normal (LLN) from pretreatment value	Withhold trametinib for up to 4 weeks. 
• If improved to normal LVEF value, resume trametinib at lower dose.• If not improved to normal LVEF value, permanently discontinue

Severity of Adverse Reaction^a	Dosage Modification for Trametinib ^b
	trametinib.
Symptomatic cardiomyopathy Absolute decrease in LVEF of greater than 20% from baseline that is below LLN	Permanently discontinue trametinib.
Ocular Toxicities	
Retinal pigment epithelial detachments (RPED)	Withhold trametinib for up to 3 weeks. 
• If improved, resume trametinib at same or lower dose.• If not improved, permanently discontinue trametinib or resume trametinib at lower dose.
Retinal vein occlusion (RVO)	Permanently discontinue trametinib.
Pulmonary	
Interstitial lung disease (ILD)/pneumonitis	Permanently discontinue trametinib.
Febrile Reactions	
Fever higher than 104°F Fever complicated by rigors, hypotension, dehydration, or renal failure	Withhold trametinib until fever resolves, then resume trametinib at same or lower dose.
Skin Toxicities	

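### The 80%-of-doses condition in section 3.1.2 has no exemption for a patient who had a DLT, so applied literally it can under-count DLTs against the 2-of-6 stopping rule

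*Combined protocol and SAP*

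**What the plan says.** Section 3.1.2 (Safety Run-In) has three sentences on who counts among the six run-in patients.

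1. The stop rule: "If ≥ 2 patients experience DLT, we will stop enrollment and will submit next amendment with new study design". It has no dose condition.
2. The replacement rule: "Subjects who do not start or do not complete the DLT observation period for reasons other than a DLT will be replaced". The sentence goes on to leave those subjects out of the evaluation. A patient who leaves because of a DLT is therefore neither replaced nor removed.
3. The dose condition, which refers to the 28-day window: "Patient will be eligible for the DLT evaluation if at least ≥ 80 percent of trametinib and HCQ scheduled doses were taken". There is no exception for a patient who had a DLT.

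The same section foresees that a patient with a DLT "may continue study treatment if toxicity could be managed by interruption of study treatment or dose reductions". Section 3.3 adds: "Doses of any investigational product that were not administered due to toxicity will not be replaced within the same cycle". Section 10.3 defines an efficacy set and a safety set but no DLT-evaluable set.

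**The concern.** An exposure threshold usually stops a patient who took too little drug from counting as evidence of safety. Such a patient, if free of DLT, says little. A patient who had a DLT is different: the event has been observed, and the missed doses are often its consequence. Section 3.1.2 makes that distinction in its replacement sentence but not in its 80% sentence.

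The 2-of-6 rule is the protocol's only numeric toxicity stopping rule. The two-stage design in section 10.2 concerns progression, and section 13.1 lists only general grounds for suspension. With six patients, leaving out one DLT can turn a count of two (stop) into one (proceed).

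**Working it through.** **Inputs.** The DLT period is 28 days (3.1.1). Trametinib is taken once daily (3.2.1), so 28 doses are scheduled. HCQ is taken twice daily (3.2.2), so 56 are scheduled. Pooled, that is 84. The rule is two or more DLTs in six patients (3.1.2). The plan states no operating characteristic for this rule, so there is no figure of its own to reproduce.

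**Doses needed.** 0.80 × 28 = 22.4, so 23. 0.80 × 56 = 44.8, so 45. 0.80 × 84 = 67.2, so 68 pooled.

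**Case 1: the patient has a DLT and completes the 28 days.** Table 4 holds both drugs until Grade 1 or less for its listed hematologic, retinal, nausea/vomiting, hepato-biliary and QTcF events, for example "Hold HCQ and trametinib. Monitor until AE resolves to Grade" 1 or less. Table 6 has trametinib-only holds such as "Withhold trametinib for up to 3 weeks", and section 3.3 says that "the dose of the other drug may not require modification per PI discretion".

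| Hold within the window | Trametinib | HCQ | Pooled | 80% met? |
|---|---|---|---|---|
| Both drugs, 5 days | 23/28 = 82.1% | 46/56 = 82.1% | 69/84 = 82.1% | Yes |
| Both drugs, 6 days | 22/28 = 78.6% | 44/56 = 78.6% | 66/84 = 78.6% | No, per drug or pooled |
| Both drugs, 7 days | 21/28 = 75% | 42/56 = 75% | 63/84 = 75% | No, per drug or pooled |
| Trametinib only, 6 days | 22/28 = 78.6% | 56/56 | 78/84 = 92.9% | No per drug, yes pooled |

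The 7-day row is realistic: Table 4 monitors the hematologic and hepato-biliary events weekly, so a hold lifted at the next weekly check costs about that long. For single-drug holds the answer depends on whether 80% is per drug or pooled, which the text does not say. Pooled, a trametinib-only hold passes up to 16 days (68/84 = 81.0%) and fails at 17 (67/84 = 79.8%). An HCQ-only hold passes up to 8 days (68/84 = 81.0%) and fails at 9 (66/84 = 78.6%).

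**Case 2: the patient leaves because of the DLT.** If both drugs stop after day 14, at most 14/28 and 28/56 doses were taken (50%). The replacement sentence keeps this patient, and the 80% sentence does not admit the patient. The same conflict arises for any permanent stop with no dose from day 23 on (at most 22/28 = 78.6%). If the last dose day is day 23, 23/28 = 82.1% passes.

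**Effect on the rule, illustration only.** The documents give neither the DLT rate p nor the share f of DLT patients who would be excluded, so both are assumed. With r the rate of counted DLTs,

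P(at least 2 of 6) = 1 − (1 − r)^6 − 6r(1 − r)^5.

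All DLTs counted: r = p. Excluded and not replaced: r = p(1 − f). Excluded and replaced: r = p(1 − f)/(1 − pf).

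| p | All counted | f = 0.25, not replaced | f = 0.50, not replaced | f = 0.50, replaced |
|---|---|---|---|---|
| 0.10 | 0.114 | 0.069 | 0.033 | 0.036 |
| 0.20 | 0.345 | 0.224 | 0.114 | 0.137 |
| 1/3 | 0.649 | 0.466 | 0.263 | 0.345 |

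For example, p = 1/3 with f = 0.50 not replaced gives r = 1/6 and 1 − (5/6)^6 − (5/6)^5 = 0.263. The last column is for comparison only, since the text does not authorise replacing a DLT patient.

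**The case against.** The best defence is that the three sentences can be read together. The stop rule is unconditional and never mentions the dose condition. The replacement sentence is the only one that expressly removes anyone from the evaluation, and it spares patients who leave because of a DLT, which goes a long way towards answering Case 2. The 80% sentence says a patient is eligible if the threshold is met, not only if. The figure mirrors the 20% missed-dose allowance in 3.2.1 and 3.2.2, which suggests an exposure test for patients without a DLT. Doses held under the protocol might also not count as scheduled. Finally, an excluded DLT would not vanish: it is documented (3.1.2), patients are discussed weekly (7.3), anyone dosed enters the safety evaluation (10.3), and section 13.1 allows suspension for unacceptable risk.

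Much of this stands. The combined reading is probably what was meant, and the fallback safeguards limit the harm. It does not remove the conflict. An eligibility test naturally excludes those who fail it. The DLT exemption in the replacement sentence makes its absence from the 80% sentence more conspicuous. The text is silent on whether held doses are scheduled. Case 1, where the patient completes the window, is not touched by the replacement sentence at all. Documenting a DLT does not put it back into the numeric count.

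**Conclusion.** The concern holds, with high confidence, and should be fixed. Section 3.1.2 does not agree with itself on which patients count toward the 2-of-6 rule, and no other section resolves it. The dose arithmetic follows from the protocol's own schedule: a 6-day hold of both drugs puts a patient below 80% on either reading, provided held doses still count as scheduled.

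This is an internal conflict that can lead to under-counting, not proof that DLTs will be missed. The loss in stopping probability rests wholly on the assumed DLT rate and excluded share. It is zero if staff count every DLT.

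**What to change.** Reconcile the sentences in 3.1.2. State that any patient with a DLT in the 28-day window is evaluable and counts toward the 2-of-6 rule whatever doses were taken, and that the 80% condition applies only to patients without a DLT. In the same place, say whether the 80% is per drug or pooled and whether doses held for toxicity count as scheduled.

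This brings the dose condition into line with the stop and replacement sentences. It costs one or two sentences, needs no extra patients, visits or data, and leaves every DLT criterion, dose and stopping threshold as it is.
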